1 PROJECT SUMMARY

Prediabetes is a precursor of type 2 diabetes and an independent risk factor for cardiovascular disease, and currently affects one-quarter of the population of the United States. Individuals of overweight or obese BMI are at particular high risk for incident diabetes. A major modifiable risk factor for type 2 diabetes is poor dietary quality, and improvement of dietary quality can effectively delay and even prevent type 2 diabetes. Interventions to improve dietary quality thus far, however, rely on short-term intensive clinically designed meals replacing the entire diet which have poor sustainability. Persistent improvements to daily dietary patterns are often difficult without directed guidance, and overall dietary quality in the United States remains poor. The identification of a practical, daily dietary intervention to improve dietary quality and prevent diabetes in those at high risk remains unknown. We propose to enroll 40 individuals with diagnosed prediabetes into a randomized controlled pilot study and provide a daily walnut supplementation intervention to determine feasibility and acceptability of the supplement. We will then determine preliminary efficacy on metabolic markers and will investigate associations between dietary quality and circulating levels of branched-chain amino acids. Our goal is to implement a whole-food supplement to improve dietary quality in patients with prediabetes as a tool for future type 2 diabetes prevention.

2 SPECIFIC AIMS AND HYPOTHESES

Aim 1: Determine a) feasibility for recruitment and retention into a randomized controlled trial of daily walnut supplementation, and b) acceptability and adherence to the intervention containing 28g of walnuts daily, compared with usual care in individuals with prediabetes.

Aim 2: Determine preliminary efficacy of the walnut intervention vs. usual care on change in a) fasting glucose, HbA1c and lipid levels, b) dietary quality score and c) BCAA and AAA levels. These estimates of efficacy will inform the sample size for a larger future randomized controlled trial.

3 SIGNIFICANCE

3.1 BACKGROUND

Over one-quarter of the adult population in the United States has prediabetes.

Prediabetes is a state of impaired fasting glucose and/or impaired glucose tolerance that is an independent risk factor for type 2 diabetes and cardiovascular disease.^{1,2} Up to 30% of people with prediabetes will progress to diabetes in 5 years at current standards.² The Diabetes Prevention Program (DPP) is an intensive diet and exercise program that has been shown to decrease incident diabetes in those with impaired glucose tolerance,³ however this intervention is cost and labor-intensive and is not available to all individuals with prediabetes. In addition, changes to diet and lifestyle must be lasting to significantly delay or prevent diabetes and its complications. The current standard of care to prevent diabetes in those with prediabetes consists only of minimal counseling during primary care visits without significant between-visit follow-up.

[figure not shown]
Dietary quality is a strong, modifiable risk factor for diabetes and cardiovascular disease. NHANES surveys reveal stably poor dietary quality in the US population over many years, despite improvements in public health messaging.⁴ In observational studies, improved dietary quality is associated prospectively with lower incidence of type 2 diabetes and cardiovascular disease.⁵⁻⁷ Modeling from a longitudinal cohort study suggests that animal protein consumption may promote progression to diabetes at a faster rate than plant-based protein intake.^{8,9} There are currently no targeted public health messages to assist those with prediabetes in refining their dietary quality with the goal of preventing diabetes.

Walnut intake has been shown to improve insulin sensitivity, decrease cardiovascular risk and improve endothelial function. Walnuts contain fiber, polyunsaturated fatty acids and plant-based protein that improve satiety.¹⁰ In conjunction with a Mediterranean diet, supplementation with walnuts has been associated with decreased risk of metabolic syndrome,¹¹ cardiovascular disease¹² and mortality^{12,13} in high-risk populations.

Plant-based protein consumption,^{8,14} and nut intake in particular, over the long-term have shown inverse associations with incident type 2 diabetes in large cohort studies.¹⁵

Individuals who regularly consume nuts have a lower BMI in epidemiologic studies,¹⁶ and feeding trials have demonstrated an improvement in lipid subfractions with acute and long-term intake of nuts.¹⁷⁻¹⁹ In short-term

Figure 1: Conceptual Model

trials, consumption of nuts improved endothelial function²⁰ and insulin signaling¹⁷ without

caloric restriction. These findings suggest that nut intake and the quality of diet has a major effect on the pathways involved in both the incidence and complications of diabetes. (Figure 1) Increasing nut consumption may also improve satiety, ideally displacing those foods, such as refined carbohydrates, that have been shown to contribute to the incidence of diabetes, cardiovascular disease and obesity.²¹

Practical, daily interventions can result in improved overall dietary quality. An approach to add walnuts to usual dietary intake, exchanging one healthful food for other unhealthful foods, has the potential to improve overall dietary quality, and, in turn, improve surrogate markers of type 2 diabetes and lipids levels. With such cumulative changes, long-term improvement in dietary quality can help to decrease progression to type 2 diabetes in people at high risk. The PREDIMED trial added either nuts or olive oil to a Mediterranean-style diet, compared to a low-fat control diet and found decreased fasting glucose and LDL levels, as well as lower clinical outcomes of incident diabetes and cardiovascular disease.^{22,23} Little prior work, however, has assessed the effects on surrogate markers for diabetes, including metabolomics, of the addition of nuts to a usual diet in the United States and in individuals with known prediabetes who are at high risk for both diabetes and cardiovascular disease.

I have examined dietary patterns and quality and their associations with risk factors for diabetes in a population of South Asian Americans, and found that a dietary pattern characterized by refined carbohydrates and high-saturated fat sweets was associated with higher insulin resistance (HOMA-IR) and lower HDL.²⁴ I have also evaluated dietary quality, as measured by the HEI-2010 score, and its association with glycemic control in women with gestational diabetes mellitus, and found that higher dietary quality is associated with improved post-prandial glycemic control ([name], *American Journal of Obstetrics and Gynecology*, submitted). I have an investigation currently underway to examine dietary quality, BCAA intake and incident gestational diabetes mellitus in women who are part of the Coronary Artery and Risk Development in Young Adults (CARDIA) longitudinal cohort study, and our preliminary results show that lower dietary quality and higher BCAA intake is associated with an increase in gestational diabetes incidence. As the preponderance of prior work has shown improved outcomes and decreased incidence of diabetes with improvements in dietary quality, we believe that the next step is to create a practical, daily intervention to aid in improving overall dietary quality.

3.2 STUDY RATIONALE

This study will add to the literature by investigating a practical, daily intervention for individuals with prediabetes to improve dietary quality and, in turn, to prevent diabetes. We will characterize novel metabolomics pathways from dietary patterns to DM incidence that may help explain the mechanism of the effect between diet and glucose tolerance in a high-risk population. In doing so, we will identify previously unknown targets to measure the preclinical effects of dietary influence on risk for diabetes.

2.3 INNOVATION

This proposed investigation will join the burgeoning movement of dietary intervention studies that are performed in a real-world environment, without highly controlled

conditions, which is more representative of dietary patterns in people at risk for metabolic disease. The approach we use differs from the current paradigm. We aim to use a whole-food supplement, easily available outside of the research or clinical environment. We also aim to investigate changes in metabolomic measures associated with walnut supplementation as an intermediate outcome. Metabolomics can reflect current conditions for pre-existing prediabetes, and we will examine how short-term interventions can affect levels of these circulating markers. These data will also help us to determine if levels of circulating amino acid levels may be useful as markers of adherence for dietary interventions beyond self-report.

4 EXPERIENCE OF THE INVESTIGATORS

[name] MPH is an Assistant Professor in the Division of General Internal Medicine at the University of California, San Francisco. Over the past 5 years, she has focused her research in the areas of dietary patterns, cardiometabolic disease, and racial/ethnic disparities. Her prior work demonstrates associations of dietary quality and patterns with risk factors for metabolic disease, in both normal weight and overweight/obese individuals, and her objective for this study is to evaluate a walnut supplementation intervention in high-risk individuals with prediabetes. Her long-term goal is to identify and implement practical dietary interventions to improve dietary quality and ultimately prevent diabetes.

5 RESEARCH DESIGN AND METHODS

5.1 Study Participants

Study Population, Study Design and Eligibility criteria: We will enroll 40 individuals with prediabetes identified through an electronic medical record query from patients in the UCSF DGIM primary care clinics and through outside recruitment in the surrounding community. We will exclude patients with tree nut or peanut allergies, who are unwilling to consume a daily nut supplement, are on dietitian-managed, restricted diets for any medical condition, have overt diabetes or are on glucose-lowering medications, or who are currently enrolled in a Diabetes Prevention Program activity. See full inclusion and exclusion criteria in next section.

5.2 Study Overview

This is a single-center, unblinded, randomized-controlled trial. 40 study subjects are planned. Each subject will consume 28g of individually wrapped raw, unsalted walnuts daily for a total of 12 weeks. Participants will be assigned to the treatments in random order. Evaluations will be taken at baseline and at end-of-study.

Screening data will be reviewed to determine subject eligibility. Subjects who meet all inclusion criteria and none of the exclusion criteria will be entered into the study.

5.3 Study Intervention

Participants in the Usual Care group and Walnuts groups will receive usual counseling and care, including general dietary and lifestyle counseling provided to all patients with diagnosed prediabetes, recommending a diet high in vegetables, fruits, whole grains, lean protein and dairy. Those in the Walnuts intervention group will receive initial dietary counseling to describe the high refined carbohydrate foods to be replaced with the

intervention walnut supplement. The intervention group will receive one, individually-wrapped, 28g packet of raw, unsalted walnuts to be consumed daily for a total of 12 weeks to replace specific high refined carbohydrate snacks. Individually packaged walnuts will be donated by the California Walnut Commission, who will not have a role in the design, procedures or interpretation of this study. Participants will be required to log their food exchanges on a daily basis. This study is designed as a non-blinded trial, therefore to protect against greater than usual consumption of walnuts by the Usual Care group during the intervention period, we will offer walnut supplementation at the end of the trial to these participants. Participants in the Usual Care group will be instructed to carry out usual diet and lifestyle changes for the 12-week duration, and will receive walnut supplementation, identical in dose and duration to the intervention group, after the completion of the study.

The following treatment regimens will be used:

- Walnuts “Now”: 28g of individually-wrapped raw, unsalted walnuts consumed daily for 12 weeks during the study period
- Walnuts “Later”: Usual diet during the study period. The participants will be provided with an equivalent amount of individually wrapped walnut packets for their daily use after the study period has concluded.

5.4 Randomization and Blinding

Randomization: Participants will be randomly assigned to two groups of 20 participants each: “Walnuts Now” Or “Walnuts Later”. We will block our randomization by two important potential confounders: sex (female or male) and age categories (<50 or \geq 50 years). We will generate stratum-specific sequential ID numbers to randomly allocate individuals to intervention groups in blocks of four. Study staff will be blinded to the linkage between ID numbers and group assignment. Upon enrollment, each participant's stratum will be identified and the next sequential ID number from that stratum was assigned. At the end of the baseline visit, the interviewer will open a sealed, opaque envelope pre-printed with the sequential ID number revealing the intervention group assignment to the participant.

Blinding

Due to the objectives of the study, the identity of test and control treatments will be known to investigators, research staff, or patients.

This study is designed as a non-blinded trial, therefore to protect against greater than usual consumption of walnuts by the Usual Care group during the intervention period, we will offer walnut supplementation at the end of the trial to these participants. Participants in the Usual Care group will be instructed to carry out usual diet and lifestyle changes for the 12-week duration, and will receive walnut supplementation, identical in dose and duration to the intervention group, after the completion of the study.

Because of the behavioral nature of the intervention, study staff who administer the intervention and study participants will not be blinded to their intervention group assignment, however we will blind the outcomes assessments – clinical labs and amino acid analyses will be done by labs without knowledge of intervention group.

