5.6 CLINICAL VISITS AND PROCEDURES

Demographics

Demographic information (date of birth, gender, race/ethnicity) will be recorded at Baseline visit.

Medical History

Relevant medical history, including history of current disease and information regarding underlying diseases will be recorded at Baseline visit.

Vital Signs

Weight, height, blood pressure and waist circumference will be collected and body mass index calculated at initial baseline visit and study completion visit.

Clinical Laboratory Measurements

Blood will be obtained by venipuncture at the UCSF Clinical Research Services site at Parnassus at baseline and study completion visits. We will obtain 4 tubes of blood (serum and plasma and separated into aliquots. One aliquot of serum will be sent to Quest Diagnostics for determination of fasting glucose, lipid Apo A1- and ApoB, s and A1c measurements. An aliquot of plasma will be sent to the West Coast Metabolomics Center at the University of California, Davis, for determination of targeted amino acid metabolomics analysis. The remaining aliquots will be frozen at -80C for future research. See Table 1 for Study procedures at each visit.

Telephone Screening

Individuals who respond to recruitment notices will be provided with a general overview of the program and will complete a brief telephone survey to determine initial eligibility (age, prediabetes diagnosis) before being invited to the screening visit.

Baseline clinic visit

At the baseline visit, the study will be explained in detail, and informed consent will be obtained. Candidates will be told that this is a trial of walnut supplementation to improve dietary quality in overweight or obese individuals with prediabetes.

The research coordinator will perform measurement of height using a stadiometer and weight using a digital scale. Those with a BMI $\geq 25 \text{ kg/m}^2$ ($\geq 23 \text{ kg/m}^2$ if of Asian or South Asian ethnicity) will be eligible. The research coordinator will then perform a capillary blood glucose measurement using an Accu-check Aviva Connect blood glucose meter and Accu-Check test strips. A capillary blood glucose value of 100mg/dL and higher will be considered eligible for participation in the study.

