6 PROTECTION OF HUMAN SUBJECTS

6.1 Risks to the Subjects

6.1.a Human Subject Involvement and Characteristics: We will be enrolling approximately 40 volunteers who are overweight or obese and who fulfill criteria for prediabetes.

Eligibility criteria are listed below:

Inclusion Criteria

1. Male or female between 18-65 years of age at baseline living in the San Francisco Bay area.
2. $BMI > 25 \text{ m/kg}^2$ (or $> 23 \text{ m/kg}^2$ for individuals of Asian or South Asian ethnicity)
3. Documentation of prediabetes diagnosis as evidenced by the following criteria:
 - a. A fasting glucose 100-125 mg/dL, or a HbA1c measurement of 5.7-6.4%, OR a diagnosis of "prediabetes" or "impaired fasting glucose" in the past 6 months, identified through an electronic medical record query from patients at UCSF and through outside recruitment in the surrounding community
 - b. We will confirm eligibility of potential participants by repeating fasting capillary blood glucose measurements at the baseline visit to ensure that they have prediabetes
4. Written informed consent and ability for subject to comply with the requirements of the study.

Exclusion Criteria

1. Pregnant or breastfeeding women at enrollment.
2. Presence of a condition or abnormality that in the opinion of the Investigator would compromise the safety of the patient or the quality of the data, such as diverticulosis or diverticulitis.
3. Tree or peanut allergies
4. Unwilling to consume a daily walnut supplement.
5. Diagnosis of diabetes
6. On glucose lowering medications
7. Dietician-managed dietary intake, or personal or medical dietary restrictions that do not allow consumption of walnuts
8. Malabsorptive conditions including intestinal bypass surgery, pancreatitis, inflammatory bowel disease

All subjects should be maintained on the same medications throughout the entire study period, as medically feasible, with no introduction of new glucose-lowering therapies.

6.1.b Sources of Materials: All personal, medical, and biochemical, data collected during the studies are for research purposes only, although test results that come from

certified laboratories can be provided to patients or their physicians upon request with the subject's permission.

6.1.c Potential Risks:

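### A single published block size of four within strata at an unblinded site makes about 29% of allocations deducible; random blocks of 4 and 6 are a cheap, optional improvement with a modest gain

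*Combined protocol and SAP*

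**What the plan says.** Section 5.2 describes the trial in these words: "This is a single-center, unblinded, randomized-controlled trial". It plans 40 participants.

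Section 5.4 sets two groups of 20, stratified by sex and by age below 50 or 50 and over, which makes four strata. It then gives the block rule: "We will generate stratum-specific sequential ID numbers to randomly allocate individuals to intervention groups in blocks of four". No section mentions a varying or undisclosed block size.

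Section 5.4 also protects the next assignment. It says "Study staff will be blinded to the linkage between ID numbers and group assignment", and on the reveal, "At the end of the baseline visit, the interviewer will open a sealed, opaque envelope". The number on the envelope is the next one in sequence for the participant's stratum.

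Once revealed, assignments are open: "the identity of test and control treatments will be known to investigators, research staff, or patients". This does not conflict with the blinded linkage, which applies before the envelope is opened.

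Outcome measurement is partly masked: "clinical labs and amino acid analyses will be done by labs without knowledge of intervention group".

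**The concern.** The envelopes and the blinded linkage prevent staff from reading the next assignment. They do not prevent staff from inferring it. In a block of four with two places per arm, once one arm has both its places filled, the rest of the block is fixed. Anyone who knows the block size and has kept count of opened assignments in that stratum then knows the next one before the participant enrolls.

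What is at stake is selection at enrollment. Age is asked at the telephone screen (section 5.6), so part of the stratum is known early. One exclusion in section 6.1 rests on judgment: "Presence of a condition or abnormality that in the opinion of the Investigator would compromise the safety of the patient". A person who foresaw the next arm would have some room there to admit or turn away a candidate. Aim 2 estimates are meant to inform the sample size of a larger trial, so the comparability of the arms has value beyond this pilot.

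**Working it through.** The plan gives no predictability figure, so there is none to reproduce.

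**Inputs from the documents.** 40 participants (5.2); 1:1 allocation, four sex-by-age strata and a fixed block of four (5.4).

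**Assumptions.** Stratum sizes are not given. The main case takes four strata of equal expected size, with the actual counts left to chance. The guesser knows the block size and every earlier assignment in the stratum.

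**One complete block of four.** There are 6 equally likely orders of two and two.

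- Probability that the allocation is certain at positions 1 to 4: 0, 0, 1/3, 1. The sum is 4/3, and (4/3)/4 = 33.3%. The third is certain only if the first two went to the same arm, which happens in 2 of 6 orders.
- Probability that the best guess is right: 1/2, 2/3, 2/3, 1. The sum is 2.833, and 2.833/4 = 70.8%.

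**Incomplete last blocks.** A last block holding 0, 1, 2 or 3 participants has 0, 0, 0 or 1/3 certain allocations. Against the full-block rate of 1/3 per participant, the shortfall is 0, 1/3, 2/3 or 2/3. If the four remainders are about equally likely, the mean shortfall is (0 + 1/3 + 2/3 + 2/3)/4 = 5/12 per stratum, or 4 × 5/12 = 1.67 over four strata.

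- Certain: 40/3 − 1.67 = 11.67, and 11.67/40 = 29.2%.
- Weighting by binomial(40, 0.25) stratum sizes gives 29.17% certain and 68.96% for the best guess, against 50% by chance.
- Simulated at the level of the participant, the mean is 11.7 of 40, with a 95% range of 9 to 15.

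**Sensitivity to stratum sizes.**

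- Shares of 40/30/20/10% give 29.15% certain and 68.95% best guess.
- Lowest over all splits of 40, for example 10/10/10/10: each stratum has two full blocks and two participants left over, so 4 × 2 × 4/3 = 10.67, and 10.67/40 = 26.7%.
- Highest, for example 8/8/12/12: all ten blocks are complete, so 10 × 4/3 = 13.33, and 13.33/40 = 33.3%.

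**Random blocks of 4 and 6.** Here the guesser knows that both sizes are possible but not which was drawn. The belief about block size and position is updated after each reveal, and an allocation counts as certain only if every remaining possibility gives the same arm. With equal expected strata this gives 6.0% certain (0.060 × 40 = 2.4) and a best guess of 67.2%. A separate simulation of 8,000 trials gave 5.9% and 67.2%.

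| | Fixed 4 | Random 4 and 6 |
|---|---|---|
| Certain allocations | 29.2% (11.7 of 40) | 6.0% (2.4 of 40) |
| Best guess right | 69.0% | 67.2% |
| Mean absolute arm-size difference | 1.31 | 1.49 |
| Exactly 20:20 | 43.3% | 39.1% |
| Difference of 4 or more | 8.3% | 12.4% |
| Difference of 6 or more | 0.3% | 1.0% |

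**The case against.** The case for leaving the scheme alone is substantial. Stratified permuted blocks with sequential numbers, a blinded linkage and opaque envelopes are a recognised method. The change lowers the best guess by only 69.0 − 67.2 = 1.8 percentage points. It also makes the arms somewhat less equal in a trial of 40 that plans 20 per group. The motive to steer is weak, since every participant receives walnuts, now or later. Eligibility depends mostly on measured BMI and capillary glucose, and the outcomes named for ANCOVA are laboratory values, adjusted for baseline and measured by blinded laboratories. All of this stands, and it limits the importance of the point. What it does not remove is certain foreknowledge of about 11.7 allocations for a person who keeps count, which needs no guessing and which the envelopes cannot prevent.

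A reader might infer that the allocation is unconcealed, or that selection is likely. The documents do not support that. They mention an interviewer, a coordinator, a research assistant and the principal investigator. They do not say who makes the telephone screen, nor that any one person has the block size, the stratum history and the enrollment decision together. The principal investigator reviews data forms and, monthly, accrual and randomization (6.5.c), but is not said to enroll.

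A reader might also infer that 5.6 contradicts 5.4, because it narrates randomization before the baseline questionnaires and blood draw, and that baseline diet recall is therefore exposed to knowledge of the arm. That does not hold either. Section 5.4 puts the reveal at the end of the baseline visit, and Table 1 lists the food frequency questionnaire among that visit's procedures. The account in 5.6 is not a strict chronology: it lists height and weight after randomization although both were already measured for eligibility, and it puts dispensing last. Any figure for a resulting shift in the dietary score would rest on assumed inputs alone, so none is given here.

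**Conclusion.** The point holds as a matter of design quality. With a known block of four and full tracking by stratum, about 29% of the 40 allocations can be deduced with certainty, and 27% to 33% whatever the stratum sizes. Random blocks of 4 and 6 reduce this to about 6% under equal expected strata, even if the guesser knows that both sizes are in use. The arithmetic is firm. The practical benefit is modest, because overall guessing accuracy hardly changes, feasibility is the main aim, the named ANCOVA outcomes are measured blind, and nothing shows that the information would be held together or used. This is a cheap and optional improvement, not a defect that threatens the trial.

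**What to change.** Before enrollment starts, generate the allocation list with block sizes drawn at random from 4 and 6 within each sex-by-age stratum. In section 5.4, say only that permuted blocks of varying size are used, and keep the sizes in a separate document that enrolling staff do not use.

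This requires one regenerated list and a small edit, with no extra visits or data. The price is slightly less even arms: the mean difference rises from about 1.3 to 1.5 participants, an exact 20:20 split becomes less likely (about 43% to 39%), and a difference of 4 or more becomes more likely (about 8% to 12%). The present scheme does not guarantee 20 per group either.

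As a matter of wording only, 5.6 could repeat the rule in 5.4 that the envelope is opened at the end of the baseline visit.
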